## LIST OF ABBREVIATIONS AND ACRONYMS

CFR	Code of Federal Regulations
CFTR	cystic fibrosis transmembrane conductance regulator
CF	cystic fibrosis
CFF	Cystic Fibrosis Foundation
CFFPR	Cystic Fibrosis Foundation Patient Registry
C.I.	confidence interval
CRF	case report form
CSBM	complete bowel movements
DIOS	distal intestinal obstruction syndrome
EDC	Electronic data capture
FDA	Food and Drug Administration
GCP	Good Clinical Practice
GI	gastrointestinal
HIPAA	Health Insurance Portability and Accountability Act of 1996
ICF	informed consent form
ICH	International Conference on Harmonisation
IRB	Institutional Review Board
NPD	Nasal potential difference
PAC-SYM	Patient Assessment of Constipation-Symptoms
PAGI-SYM	Patient Assessment of Gastrointestinal-Symptoms
PAC-QOL	Patient Assessment of Constipation Quality of Life
PAGI-QOL	Patient Assessment of Gastrointestinal-Symptoms Quality of Life
PEG	polyethylene glycol
PI	Principal Investigator
PRO	patient reported outcome
PROMIS	FDA patient-reported outcomes measures
PROs	patient reported outcome surveys
QOL	Quality of Life
SIBO	small intestinal bacterial overgrowth
TDNCC	Therapeutics Development Network Coordinating Center

## PROTOCOL SYNOPSIS

TITLE	Multicenter study of patient-reported gastrointestinal symptoms in people with Cystic Fibrosis (GALAXY)
SPONSOR-INVESTIGATOR	A. [name], MSc (Emory University/Children's Healthcare of Atlanta) [name] (University of North Carolina Charlotte, Atrium Health) [name] (University of Texas Southwestern/Children's Health)
FUNDING ORGANIZATION	Cystic Fibrosis Foundation (CFF)
NUMBER OF SITES	Approximately 26
RATIONALE	There are currently no large, multicenter prospective clinical trials examining management of constipation or other gastrointestinal (GI) symptoms in people with cystic fibrosis (CF). Current recommendations in the CF literature are largely based on expert consensus and opinions. Yet, constipation and other GI symptoms are crucial factors in quality of life (QOL) and maintenance of optimal nutritional state in people with CF. This study will use GI-symptomatology questionnaires to understand the multiple overlapping GI symptoms in people with CF. This would be followed by studies to improve GI outcomes through establishing evidence-based algorithms, starting with constipation. In the future, we would also like to evaluate the impact of CF modulators on common GI symptoms and evaluate how this might impact the development of symptom-specific algorithms.
STUDY DESIGN	This is a prospective, multicenter, observational study designed to collect gastrointestinal related data in patients with CF.  Eligible subjects will be consented and enrolled in the study at the Enrollment Visit. At the visit, the subject or parent/guardian will complete the patient reported outcome surveys (PROs) using their mobile device (e.g., smartphone or tablet). The PROs will consist of four questionnaires: Patient Assessment of Constipation-Symptoms (PAC-SYM), Patient Assessment of Gastrointestinal-Symptoms (PAGI-SYM), Patient Assessment of Constipation Quality of Life (PAC-QOL) and the disease-specific questionnaire. The disease-specific questionnaire will include the Bristol Stool Scale and will collect information on presence of fecal incontinence, stool quality and stool frequency. At the Enrollment Visit, weight and height will be collected in addition to medical history and concomitant medication information. The subject or parent/guardian will complete the PROs outside-the-clinic setting per the Schedule of Events using their mobile device.

DURATION OF SUBJECT PARTICIPATION AND DURATION OF STUDY	Subjects will be on study for up to 29 days. The total duration of the study is expected to be approximately 13 months: 12 months for subject recruitment and 1 month for the final subject enrolled to complete the study.
PRIMARY OBJECTIVE	Assess the feasibility of electronic PROs conducted outside-the-clinic.
SECONDARY OBJECTIVES	
 
▪ Estimate the prevalence and variability of GI symptoms occurring in pediatric and adult patients with CF
 
▪ Describe current management of GI symptoms in patients with CF
 
▪ Gather information to guide and inform on the design of future algorithm-based approaches to treating GI symptoms in people with CF
 

NUMBER OF SUBJECTS	Up to 400
SUBJECT SELECTION CRITERIA: Inclusion Criteria	
 
1. All genders <math>\geq</math> 2 years of age at time of consent
 
2. Documentation of a Cystic Fibrosis (CF) diagnosis as evidenced by one or more clinical features consistent with the CF phenotype and one or more of the following criteria: 
 
▪ Sweat chloride equal to or greater than 60 mEq/liter by quantitative pilocarpine iontophoresis test (QPIT)
 
▪ Two well-characterized mutations in the cystic fibrosis transmembrane conductance regulator (CFTR) gene
 
▪ Abnormal nasal potential difference (change in NPD in response to a low chloride solution and isoproterenol of less than -5 mV)
 
 
 
3. Enrolled in the Cystic Fibrosis Foundation Patient Registry (subjects may enroll in the Registry at Enrollment Visit if not previously enrolled)
 
4. Written informed consent (and assent when applicable) obtained from subject or subject's legal representative
 
5. Willing to complete questionnaires on mobile device
 
6. Able to use the Medidata Patient Cloud mobile application for completing the questionnaires
 

SUBJECT SELECTION CRITERIA: Exclusion Criteria	
 
1. Presence of a condition or abnormality that, in the opinion of the Investigator, would complicate interpretation of study outcome data or interfere with achieving the study objectives
 
2. Presence of a pulmonary exacerbation at the Enrollment Visit
 
3. Hospitalization for distal intestinal obstruction syndrome (DIOS) within the 28 days prior to the Enrollment Visit
 
4. Current gastrointestinal (GI) or abdominal/pelvic malignancy
 
5. Abdominal or pelvic surgery within the 28 days prior to the
 

	
Enrollment Visit
 
 
6. At the time of the Enrollment Visit, planned abdominal or pelvic surgery or bowel cleanout in the 28 days after the Enrollment Visit
 
7. Initiation of new CFTR modulator therapy within the 4 weeks prior to the Enrollment Visit
 
8. Intent to initiate new CFTR modulator therapy within 28 days of the Enrollment Visit
 

TEST PRODUCT, DOSE, AND ROUTE OF ADMINISTRATION	Not applicable
CONTROL PRODUCT, DOSE AND ROUTE OF ADMINISTRATION	Not applicable
CONCOMMITANT MEDICATIONS	
Allowed: Standard therapy for CF is allowed.
 
Prohibited: There are no prohibited medications.

PRIMARY ENDPOINT	Percentage of scheduled outside-the-clinic assessments with at least one of the four PROs fully completed.
SECONDARY ENDPOINTS	
Assess the feasibility of electronic PRO surveys conducted outside-the-clinic setting:
 
 
1. At each scheduled outside-the-clinic assessment, number (%) of subjects with at least one PRO fully completed
 
2. For each PRO, number (%) of subjects with fully completed questionnaires at each scheduled outside-the-clinic assessment and overall
 
3. Number (%) of completed PROs by subject, site, and other demographic and clinical features
 
 
Estimate the prevalence and variability of GI symptoms:
 
 
▪ Evaluate prevalence of protocol-defined constipation:           
 
4. Number (%) of enrolled subjects with any occurrence of constipation during 1 month of follow-up (the period prevalence)
 
 
 
▪ Evaluate frequency and severity of each GI symptom at scheduled assessments and overall:           
 
5. Number (%) of subjects with presence of GI symptom
 
6. Distribution of severity scores of GI symptom
 
7. Mean severity score of GI symptom
 
8. Distribution of stool frequency and type by Bristol Stool Scale
 
9. Change in distribution of GI symptoms and stool frequency/type from enrollment visit overall and by whether
 
 
 

	
subjects were receiving treatment
 
 
▪ Evaluate PRO scores overall and by sub-scale at scheduled assessments:           
 
10. Mean PRO score
 
11. Within and across subject variability of PRO scores
 
12. Mean PRO scores (also mean differences and 95% confidence interval) comparing subjects with constipation to those without constipation
 
 
 
▪ Evaluate alternative CF specific definitions of constipation:           
 
13. Examine alternative definitions of constipation that are CF specific based on correlation with PRO questionnaires and maximizing the area under the receiver operating characteristic curve (ROC curve) for PAC-SYM scores
 
14. Number (%) reporting constipation based on patient self-assessment. Examine concordance of self-reported constipation against protocol/alternate definitions using Cohen's kappa coefficient
 
 
 
 
Describe current management of GI symptoms:
 
 
▪ Evaluate treatment for GI symptoms and constipation at time of enrollment visit:           
 
15. Number (%) of all subjects receiving treatment
 
16. Number (%) of all subjects initiating treatment
 
17. Number (%) of all subjects receiving treatment by Medication class/type
 
18. Among subjects with GI symptoms and constipation, number (%) receiving treatment
 
 
 
▪ Evaluate symptom scores due to treatment:           
 
19. Mean PRO scores (also mean differences and 95% confidence interval) comparing subjects receiving treatment for GI symptoms to those not receiving treatment
 
20. Among subjects receiving treatment for constipation, mean absolute change in PRO scores over time overall and by medication type/class
 
 
 

PLANNED INTERIM REVIEW	
When 100 subjects have enrolled, an interim review will be conducted by an External Advisory Committee to determine whether the study should continue or stop. The Advisory Committee decision to continue to enroll or stop will be made in consideration of several factors including but not limited to: overall rate of enrollment, adequate representation of sub-populations, missing PRO data, and prevalence of constipation as well as estimates of PRO variability. The two stage enrollment strategy will allow for enriching enrollment based on either under-enrolled sub-populations or on the observed variability of GI symptoms for demographics-related factors such as

	age-group (pediatric/adult), modulator use or pancreatic status. In addition to the interim review, the TDNCC will continuously monitor enrollment and provide the Advisory Committee quarterly reports of enrollment demographics.
STATISTICS Primary Analysis Plan	
The analysis population consists of all eligible subjects who enroll into the study. Results will be based primarily on descriptive statistics of questionnaire results. The primary endpoint is the percentage of scheduled outside-the-clinic assessments with at least one PRO fully completed out of the four questionnaires administered (the PAC-SYM, PAGI-SYM, PAC-QOL and the disease-specific questionnaire). The denominator for the percentage is the expected number of outside-the-clinic assessments (# of enrolled subjects x 3 outside-the-clinic assessments/subject). Missing PRO data will be extensively summarized including a comparison of the representativeness of the enrolled subjects against the larger CF community.
 
Constipation is defined as <3 bowel movements in the past week and/or Bristol Stool type 1 or 2. The secondary endpoint upon which the sample size is based is the number (%) of enrolled subjects with any occurrence of constipation during 1 month of follow-up. For all percentages, the 95% Confidence Interval (95% C.I.) will be calculated using the Wilson method. Summary statistics of stool frequency and type will be tabulated over time to evaluate overall disease fluctuation.
 
Individual item responses will be summarized by the number and percentage having symptoms or receiving treatment. Questionnaire scores, overall as well as by subdomain, will be based on mean scores (and 95% C.I.s) with any group comparison made via the t-test. For subjects either receiving treatment or with constipation, mean absolute change in scores from the enrollment visit will be reported including the standard deviation and 95% C.I. of the change. For select endpoints, stratification by whether the site did or did not receive DIGEST Awards (CFF grant to a gastroenterologist to focus on the comprehensive GI care of patients with CF) will be considered. Additional stratification variables include: age, CF genotype, and pancreatic status.
 
To evaluate change in PRO scores, a covariate adjusted repeated measures model of PRO scores will be fit in addition to select graphical figures showing PRO scores at scheduled assessments. No adjustment for multiplicity testing will be made. The details of all planned analyses will be outlined in the Statistical Analysis Plan (SAP).

Rationale for Number of Subjects	Sample size estimates for this study are based on two criteria: 
 
1. To assess feasibility and ensure representativeness of the
 

	
enrolled CF subjects
 
2. To estimate prevalence of GI symptoms (specifically constipation)
 
The sample size estimate for this study is based on a period prevalence of constipation (the proportion of subjects with occurrence of symptom over a 1 month interval of time) in the 20% - 30% range (25% average). Approximately 400 subjects will be needed to estimate a 25% prevalence of constipation with a 95% C.I. half-width of 4.5% (95% C.I. = 20.5%, 29.5%) and assuming a 12% missing data rate. With 400 subjects, this study will allow estimation of variability (between and within subject) in 160 pediatric subjects and 240 adult subjects (alternatively 40 pediatric and 60 adults for 100 subjects).

--	--

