### **12.2 Replacement of Subjects**

Subjects who withdraw from the study will not be replaced.

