### 15.3 Analysis of Primary Endpoint

The primary endpoint is the percentage of scheduled outside-the-clinic assessments with at least one PRO fully completed out of the four questionnaires administered (the PAC-SYM, PAGI-SYM, PAC-QOL and the disease-specific questionnaire). The denominator for the percentage is the expected number of outside-the-clinic assessments (# of enrolled subjects x 3 outside-the-clinic assessments/subject).

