## 15.7 Sample Size

[figure not shown]
Sample size estimates for this study are based on two criteria:

- a. To assess feasibility and ensure representativeness of the enrolled CF subjects
- b. To estimate prevalence of GI symptoms (specifically constipation)

Period prevalence is defined as the proportion of subjects with symptom over an interval of time. Estimates of constipation prevalence in CF patients varies in the literature. A recent 2017 publication (7) showed the period prevalence of constipation over 3 months was 31% (32% adults; 30% children). Another 2010 publication (3) estimated prevalence of constipation in CF patients age  $\leq$  18 years in the Netherlands at 20% (annual assessment) using the ESPGHAN definition. Note that an epidemiologic review of constipation prevalence in the general population (non-CF) in North America ranged from 1.9% to 27.2% with most estimates from 12%-19% (19). Therefore, 10% will serve as the lower bound estimate of constipation prevalence. The sample size estimate for CF patients in the GALAXY study is based on a prevalence of constipation over a 1 month period in the 20% - 30% range (25% average).

Sample size estimates are based on 95% confidence intervals (C.I.) half-widths (i.e., width of one arm of the 95% CI) for proportions. While constipation is one symptom of interest, it is difficult to specify an exact prevalence estimate over a 1 month period utilizing the study specific definition of constipation. In addition, the occurrence of other GI symptoms is also of interest and will occur at varying rates. Therefore, the figure below shows what the sample size (y-axis) is for varying half-width sizes (x-axis) when prevalence estimates range between 10% to 50% (maximum). Approximately 400 subjects are needed to estimate a prevalence of constipation of 25% with a 95% C.I. half-width of 4.5% (95% C.I. = 20.5%, 29.5%) and assuming a 12% missing data rate.

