2.3 Definition of the Analysis Populations

Enrollment:

An enrolled participant was defined as a participant who had met all eligibility criteria, and fully completed (i.e. no question left unanswered) at least one of the ePRO questionnaires (PAC-SYM, PAGI-SYM, PAC-QOL, and disease-specific) at baseline.

Baseline:

Baseline refers to the enrollment visit of enrolled participants, at which informed consent was given, eligibility was met, and medical history was collected.

Follow-up weeks:

GALAXY Statistical Analysis Plan 12/16/2019 - CONFIDENTIAL

Follow-up occurred at week 1 (day 7, +1), week 2 (day 14, +1), and week 4, (day 28, +1). These were outside-of-clinic, i.e. participants are asked to complete the ePRO via their mobile devices. The questionnaires took approximately 10 minutes to complete. For participants \geq 2 years of age to $<$ 12 years of age, the parent/guardian completed the questionnaire. For participants \geq 12 years of age, the participant completed the questionnaire.

Protocol-defined constipation:

Per protocol, constipation is defined as $<$ 3 bowel movements in the past week and/or Bristol Stool type 1 or 2.

3. Overview of Planned Analyses

Unless otherwise noted, the endpoints of this study are mostly descriptive, with all continuous outcomes such as symptom severity and PRO scores evaluated using descriptive statistics such as mean, median, standard deviation, and 95% confidence intervals. Presence/absence of symptoms will be shown as percentages and corresponding 95% confidence intervals calculated using the Wilson method. Longitudinal models will be mixed-effect models with participant-specific random effect and compound symmetry covariance structure. Except where otherwise noted, all tests will be two-sided and statistical significance will be determined at the 0.05 level. No adjustment for multiple comparisons will be made.

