3.3 Primary Endpoint

GALAXY Statistical Analysis Plan 12/16/2019 - CONFIDENTIAL

The primary endpoint of the study is the percentage of scheduled out-side-the-clinic assessments with at least one of the four PROs fully completed. Subgroup analysis on the primary endpoint is performed by age group.

The analysis on the primary endpoint is summarized in Appendix A, Section A.3.

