		Protocol-Defined Constipation at Baseline		All Enrolled Participants (N=n)	Fully Completed at Least One ePRO at all Follow-up Weeks (N=n)	CF Registry (N=n)
		Yes (N=n)	No (N=n)			
Genotype, n (%)	F508 Heterozygous F508 Homozygous Other/Unknown					
Mutation Class, n (%)	I-III IV-V Unknown					
Sweat Chloride at Diagnosis (mEq/L)	Mean (SD)					
Weight (kg)	Mean (SD)					
Height (cm)	Mean (SD)					
Pancreatic Sufficiency[1], n (%)	Insufficient Sufficient Unknown					
Modulator Use, n (%)	None Ivacaftor Ivacaftor/Lumacaftor Ivacaftor/Tezacaftor Ivacaftor/Tezacaftor/Elexacaftor					

[1] Pancreatic Insufficient is defined as PERT use and/or fecal elastase or other diagnostic test at baseline.
Note on missing demographic data

Exhibit 5.2.2 Summary of Period-Prevalence of Constipation with Disease-Specific Questionnaire Fully Completed at all Weeks

This table summarizes the period-prevalence of protocol-defined constipation, as well as other definitions of constipation. Only participants who fully completed the disease-specific questionnaire at baseline and all follow-up weeks were considered. Period prevalence is defined as occurrence of the symptom at any time from baseline to week 4.

	Age <18 Years (N = n)	Age ≥18 Years (N = n)	All Participants (N = n)
Protocol-Defined Constipation ^[1] :	% (95% CI)		
Self-Described Constipation ^[2]			
Constipation			
Alternating Constipation and Diarrhea			
Alternative Definition:			
Definition 1			
...			
Definition d			

[1] Protocol-defined constipation is defined as less than 3 bowel movements and/or Bristol Stool type 1 or 2 in the past week

[2] Self-described constipation is based on the second question on the disease-specific questionnaire

Note: See Appendix B for discussion regarding alternative definitions of constipation.

Exhibit 5.2.3 Summary of Period-Prevalence of Constipation with Disease-Specific Questionnaire Fully Completed at least once

Similar table as above with consideration of participants who fully completed the disease-specific questionnaire at least once.

Exhibit 5.3.1 Summary of GI Symptoms from PAC-SYM, PAGI-SYM, and PAC-QOL

This table summarizes the GI symptoms based on prespecified questions from PAC-SYM, PAGI-SYM, and PAC-QOL questionnaires. All questions were based on patient's experience in the last week.

	Baseline	Week 1	Week 2	Week 4	Overall [1]
Symptom 1					
N [2]					
Absent, n (%)					
Mild, n (%)					
Moderate, n (%)					
Severe, n (%)					
Very Severe, n (%)					

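### The synopsis's Wilson 95% CI for all percentages is too narrow for the primary completion percentage (three assessments per participant), and the SAP neither withdraws nor replaces it

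*Protocol*

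**What the plan says.** The statistics section of the protocol synopsis defines the primary percentage over assessments and then, in its next paragraph, sets a general rule: "For all percentages, the 95% Confidence Interval (95% C.I.) will be calculated using the Wilson method". Protocol 15.3 repeats the assessment-level denominator: "The denominator for the percentage is the expected number of outside-the-clinic assessments (# of enrolled subjects x 3 outside-the-clinic assessments/subject". It names no interval.

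Protocol 15.1 and SAP section 3 are narrower. The SAP sentence reads: "Presence/absence of symptoms will be shown as percentages and corresponding 95% confidence intervals calculated using the Wilson method". SAP 3.3 restates the endpoint ("The primary endpoint of the study is the percentage of scheduled out-side-the-clinic assessments with at least one of the four PROs fully completed") and adds a subgroup analysis by age, again without an interval method. The Exhibit 3.1 shell shows n (%) only.

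Elsewhere the SAP does allow for repeated measurement on one person: "Longitudinal models will be mixed-effect models with participant-specific random effect and compound symmetry covariance structure". That covers the PRO scores, and Exhibits 6.4 and 6.5 use participant random effects for clearance and emergence of constipation. Nothing similar is planned for completion.

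**The concern.** A Wilson interval is derived for independent binary outcomes. Here each participant contributes three, and the design pushes them to agree. Protocol 12.2 says "Subjects who withdraw from the study will not be replaced", yet such a participant still counts three times in the fixed denominator. One early withdrawal can therefore add up to three linked failures. With positive correlation, 1,200 assessments carry less information than 1,200 independent outcomes, and the interval overstates precision.

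Feasibility is the only primary objective. In a descriptive study the estimate and its interval are the main result, and planners of later electronic PRO studies would rely on both.

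**Working it through.** **Inputs from the documents.** 400 participants (100 if enrollment stopped at the interim review); 3 outside-the-clinic assessments each; 95% confidence; planned split of 160 pediatric and 240 adult participants (Protocol 15.7).

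**Assumptions.** ICC of completion from 0.1 to 0.7. Completion of 85%, or 88% as the complement of the protocol's sample-size assumption ("assuming a 12% missing data rate"), which was made for the prevalence calculation and not for completion.

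**The plan's own figure.** For 25% prevalence and a half-width of 4.5 points, n = 1.96² × 0.25 × 0.75 / 0.045² = 355.7, so 356, and 356 / 0.88 = 405. In the other direction, 400 × 0.88 = 352 gives a half-width of 4.5 points. The stated figure of about 400 reproduces. That calculation has one outcome per participant, so it is not affected.

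**Primary percentage.** With three outcomes per participant and a fixed denominator, the design effect is DEFF = 1 + (3 − 1) × ICC, and the effective sample size is 1,200 / DEFF. The Wilson half-width is z / (1 + z²/n) × √(p(1 − p)/n + z²/(4n²)). The approximate coverage of the unadjusted interval is 2Φ(1.96/√DEFF) − 1.

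| ICC | DEFF | Effective n | Half-width, 85% (points) | Half-width, 88% (points) | Coverage, formula | Coverage, simulated at 85% |
|---|---|---|---|---|---|---|
| 0 (plain Wilson) | 1.0 | 1,200 | 2.02 | 1.84 | 95.0% | 95.0% |
| 0.1 | 1.2 | 1,000 | 2.21 | 2.02 | 92.6% | 93.3% |
| 0.3 | 1.6 | 750 | 2.56 | 2.33 | 87.9% | 88.2% |
| 0.5 | 2.0 | 600 | 2.86 | 2.60 | 83.4% | 84.0% |
| 0.7 | 2.4 | 500 | 3.13 | 2.85 | 79.4% | 80.2% |

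The simulation was beta-binomial, 400 participants × 3, 6,000 runs. The coverage columns are for plain Wilson on n = 1,200 when the true ICC is as shown. A separate run at 88% (20,000 runs) gave 93.7, 88.7, 84.4 and 80.6% at ICC 0.1, 0.3, 0.5 and 0.7.

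**Which ICC is plausible.** Suppose a share w of participants never answers after enrollment and the rest answer each time with probability q = 0.88/(1 − w), so that overall completion is 88%. Then ICC = w(1 − w)q² / (0.88 × 0.12).

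| Part of the 12% due to never-responders | w | ICC | DEFF | Coverage |
|---|---|---|---|---|
| One quarter | 0.03 | 0.23 | 1.45 | 90% |
| One half | 0.06 | 0.47 | 1.94 | 84% |
| Three quarters | 0.09 | 0.73 | 2.45 | 79% |

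**Smaller denominators.** For the 160 pediatric participants at 85%, plain Wilson on 480 assessments has a half-width of 3.2 points. With effective n of 480/1.6 = 300 (ICC 0.3) it is 4.0, and with 480/2.4 = 200 (ICC 0.7) it is 4.9. If the study stopped at 100 participants with 88% completion, it is 3.7 points against 4.0, 4.7, 5.2 and 5.7 at ICC 0.1, 0.3, 0.5 and 0.7.

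**Does a remedy work?** In the simulations at 85%, Wilson with the effective sample size estimated from the data covered 94.7% to 95.4%. Across completion rates of 75% to 95% it covered 94.6% to 95.5%.

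**The case against.** The best defense is that no such interval is really planned. The synopsis defers to the SAP for detail, and the SAP says that it holds all modifications to the protocol's analyses. It confines Wilson to symptoms and shows completion as n (%), whereas Exhibit 5.2.2 shows a 95% CI where one is wanted. The synopsis sentence itself sits in the paragraph on constipation prevalence, where Wilson is sound. On this view the fault is a mismatch between documents, not a wrong method.

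This is a fair reading, but it does not settle the matter. The synopsis rule covers every percentage, and nothing in the SAP withdraws it for the primary one. If it stands, the interval is too narrow. If it does not, the primary estimate has no stated precision and the two documents disagree without saying so. Either way the SAP has to state which applies.

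It is also true that the size rests on an assumed ICC. Enrollment as the SAP defines it requires a completed baseline questionnaire, participants must be willing and able to use the application, and reminders are sent. These features make complete non-response less likely and argue against taking the highest ICC values as typical. They do not make a participant's three outcomes independent.

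**Conclusion.** The concern holds. Applied as the synopsis states it, Wilson gives the primary percentage an interval that is too narrow for any positive within-participant correlation, and the SAP supplies no valid replacement. With 400 participants the correct interval is about 10% wider at ICC 0.1 and about 55% wider at ICC 0.7. That is roughly 0.2 to 1.1 points of half-width at 85% completion. Both the ICC and the completion rate are assumptions. The conclusion that the correlation is positive rests on the fixed denominator and on withdrawals not being replaced.

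The consequence is limited to stated precision: the endpoint is descriptive and no success threshold is set. Percentages that count each participant once are not affected. These include completion at a single visit and period prevalence, for which the SAP says "Period prevalence is defined as occurrence of the symptom at any time from baseline to week 4". The Overall symptom-presence percentage in Exhibit 5.3.1 pools participant-weeks. It would share the problem only if the general Wilson sentence in SAP section 3 were applied to it, since its shell shows n (%) only.

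**What to change.** In SAP sections 3 and 3.3, state whether the primary percentage is reported with a 95% CI. If it is, cluster it on participant, overall and in the two age subgroups. Suitable methods are a cluster-robust or GEE variance, a participant-level bootstrap, or Wilson with effective sample size p(1 − p)/SE², where SE is the clustered standard error. The primary point estimate stays the same.

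Keep plain Wilson for percentages that count each participant once, including Exhibits 5.2.2 and 5.2.3. If an interval is added to any other percentage pooled over weeks, such as Exhibit 5.3.1 Overall, use the same clustered variance around the pooled percentage. Averaging participant proportions there would reweight the estimate, because participants answer in unequal numbers of weeks.

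The cost is two sentences in the SAP, a few lines of code and a wider reported interval. No further data are needed.
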